
with approval from the Safety Committee.
 

• 1 of 3 patients within a cohort experiences a DLT, then up to 3 additional patients are to be enrolled sequentially at that dose level. If none of the additional 3 patients has a DLT (i.e., 1 of 6 patients has a DLT), then enrollment at the next scheduled dose may commence with approval from the Safety Committee.

• If <math>\geq 2</math> patients within a cohort experience a DLT, then the DLT dose level will have been reached and the previous lower dose level will be considered the MTD. (If <math>\geq 2</math> patients in the initial dose cohort experience DLTs, then the dose will be reduced to one level lower and the same procedure will be followed.)

 
A total of 6 patients are planned to be treated at the MTD to confirm the RP2D before enrollment of patients in Phase 2 of the study. If the MTD is not confirmed at this stage, the dose will be reduced to one level lower and the same procedure will be followed.
 
Note that enrollment in the next dose cohort can begin only when the last patient enrolled in the current dose cohort completes the study through engraftment without a <math>\geq</math>Grade 3 toxicity or through 30 days post-ASCT without a DLT, whichever occurs first, provided that <math>< 2</math> patients in the current dose cohort experienced a DLT.
 
Although decisions regarding dose escalation will be made based on review of data through Day 30 post-ASCT, safety data will also be collected from all patients continuing in the study and this will be reviewed periodically by the Safety Committee. Any detected toxicity may necessitate further refinement of the RP2D.
		

Definition of MTD:
 
The MTD is defined as the highest dose level at which <math>\leq 1</math> of 6 patients experiences DLT through 30 days post-ASCT.
		

Definition of RP2D:
 
The RP2D may be equal to or higher than the preliminary MTD, but less than the non-tolerated dose (i.e., the dose at which <math>\geq 2</math> of 6 patients experienced DLT). The RP2D will be determined in discussion with the Sponsor, Medical Monitor, and Investigators.
		

Name of Sponsor Mundipharma-EDO GmbH		
Name of Finished Product: Tinostamustine hydrochloride (Formerly EDO-S101)		Name of Active Ingredient: Tinostamustine hydrochloride

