## **6.9. Safety Committee**

A Safety Committee will be involved in the conduct of this study. The Safety Committee will be comprised of Sponsor personnel, the Medical Monitor, the Investigator or representative thereof at each active study center, and a biostatistician (as needed). Ad hoc participants may be part of the committee at the request of the Sponsor or other Safety Committee members. The Safety Committee has the responsibility for monitoring the clinical study's progress and the safety of the participating patients. The Safety Committee will evaluate study conduct during the course of the clinical study, based upon data defined for this clinical study.

In Phase 1, the Safety Committee will review all safety data from all patients enrolled in each cohort to confirm any DLTs that were experienced and make a determination regarding enrollment in the next cohort. If a DLT necessitates enrollment of additional patients into a cohort, the Safety Committee will review all of the safety data for that cohort after those additional patients before a determination regarding enrollment in the next cohort is made. Based on evaluation of the data, the Safety Committee may decide that enrollment at an intermediate dose level not specified in this protocol may take place.

*Mundipharma-EDO GmbH  
Clinical Study Protocol EDO-S101-1004  
Version 2.0, 18 June 2018*

---

In addition, after identification of the MTD, the Safety Committee will review all safety data collected to date to confirm that no unexpected, significant, or unacceptable risk to patients enrolled in the study has been discovered.

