### **7.5.1. Dose Escalation Procedure**

In Phase 1, up to 3 patients initially are to be enrolled in each cohort. The first patient enrolled in the initial cohort must complete the study through engraftment without a  $\geq$ Grade 3 toxicity or through 30 days post-ASCT without a DLT, whichever occurs first, before additional patients may be enrolled in that initial cohort. (If the first patient experiences a DLT, then a lower dose will be explored for the second patient and so on.)

- If the first patient does not experience a DLT (see [Section 7.5.2](#)) or experiences engraftment without a  $\geq$ Grade 3 toxicity, the next 2 patients may be enrolled simultaneously.

After 3 patients in a cohort complete the study through engraftment without a  $\geq$ Grade 3 toxicity or through 30 days post-ASCT without a DLT, whichever occurs first, and have safety evaluations performed through that time, and:

- None of these 3 patients experience a DLT (see [Section 7.5.2](#)), then enrollment of the next cohort may commence with approval from the Safety Committee.
- 1 of 3 patients within a cohort experiences a DLT (see [Section 7.5.2](#)), then up to 3 additional patients are to be enrolled sequentially at that dose level. If none of the additional 3 patients has a DLT (i.e., 1 of 6 patients has a DLT), then enrollment at the next scheduled dose may commence with approval from the Safety Committee.
- If  $\geq 2$  patients within a cohort experience a DLT (see [Section 7.5.2](#)), then the DLT dose level will have been reached and the previous lower dose level will be considered the MTD. (If  $\geq 2$  patients in the initial dose cohort experience DLTs, then the dose will be reduced to one level lower and the same procedure will be followed.)

A total of 6 patients are planned to be treated at the MTD to confirm the RP2D before enrollment of patients in Phase 2 of the study. If the MTD is not confirmed at this stage, the dose will be reduced to one level lower and the same procedure will be followed.

Note that enrollment in the next dose cohort can begin only when the last patient enrolled in the current dose cohort completes the study through engraftment without a  $\geq$ Grade 3 toxicity or through 30 days post-ASCT without a DLT, whichever occurs first,, provided that <2 patients in the current dose cohort experienced a DLT.

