Although decisions regarding dose escalation will be made based on review of data through Day 30 post-ASCT, safety data will also be collected from all patients continuing in the study and this will be reviewed periodically by the Safety Committee. Any detected toxicity may necessitate further refinement of the RP2D.

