### **7.5.2. Definition of Dose-limiting Toxicity**

Toxicity will be assessed by the Investigator using the US NCI Common Terminology Criteria for Adverse Events (CTCAE), version 4.03. The centralized laboratory assessment of ECGs will be used for the determination of DLT.

In Phase 1 of the study, DLT is defined as the occurrence of any of the following events occurring within 30 days post-ASCT that are considered by the Investigator to be at least possibly related to tinostamustine:

- Delayed engraftment ( $>30$  days after ASCT). Engraftment will be considered delayed if the subject has not met criteria for both neutrophil and platelet engraftment:
  - Neutrophil engraftment is defined as the first of 3 consecutive days with ANC  $>0.5 \times 10^9/L$ .
  - Platelet engraftment will be defined as the first of 3 consecutive days of platelet count  $>20 \times 10^9/L$  without platelet transfusion in the prior 7 days.
- QTcF  $>500$  msec or  $>60$  msec increase from baseline, with a duration of  $>30$  minutes, based on the mean of triplicate 12-lead ECGs, or  $\geq$ Grade 3 QTcF interval prolongation accompanied by ventricular arrhythmia.

Baseline QTcF interval will be the mean value determined during triplicate ECG(s) at Day -1 (-1), before study drug administration confirmed by the central laboratory.

- Grade 4 non-hematologic toxicity
- Grade 3, non-hematologic toxicity related to treatment, **with the exception of:**
  - Nausea or vomiting
  - Diarrhea
  - Fatigue, dehydration, or glucose intolerance

- Skin rash, dry skin, or pruritus responsive to topical or systemic steroids
- Fever ( $>40^{\circ}\text{C}$  for  $\leq 24$  hours)
- Infection
- Dyspnea, hypoxia, or pneumonitis
- Abdominal pain
- Dysphagia, oral mucositis, oral pain, or anorexia
- Flu-like syndrome
- Engraftment syndrome
- Weight loss
- Pain, pain in extremity, headache, or insomnia
- Hypocalcemia, hypokalemia, hypomagnesemia, hyponatremia, or hypophosphatemia
- Increased aspartate aminotransferase (AST), alanine aminotransferase (ALT), bilirubin, or alkaline phosphatase
- Alopecia

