#### **7.5.3. Definition of Maximum Tolerated Dose**

The MTD is defined as the highest dose level at which  $\leq 1$  of 6 patients experiences DLT through 30 days post-ASCT.

[figure not shown]

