**Possible Risks Include:**

- Myelosuppression (thrombocytopenia, leukopenia, and neutropenia)
- Anemia

- *Gastrointestinal symptoms (nausea, vomiting, diarrhea, constipation)*
- *Cough*
- *Peripheral edema*
- *Pyrexia*
- *Decreased appetite*
- *Dyspnea*
- *Headache*
- *Asthenias*
- *Allergic reaction*
- *Infection*
- *QTc Prolongation*

*As noted above, the risks associated with the treatment with Tinostamustine are expected to be similar to other alkylators, like bendamustine. Additionally, patients undergoing any high-dose conditioning for transplant, will experience myelosuppression, which puts the patients at a higher risk for infection. Thus, the protocol was designed around current standard practices for monitoring the toxicity and safety of patients in this treatment setting. Patients are evaluated daily for hematologic parameters, signs of infection, and any other adverse reactions until engraftment is reached. After engraftment the patients are monitored monthly through 130 days but may be seen in between these timepoints if clinically indicated. Cardiac safety is monitored pre-infusion through 24 hours post infusion with a continuous holter monitor, in addition to ECGs being performed and read by the qualified site personnel before, during, and after the infusion. Other adverse reactions will be continuously monitored and treated as appropriate according to the protocol and local standard of care.*

*Since the purpose of this study is to evaluate the safety and preliminary efficacy of this regimen, it is unknown if this treatment will benefit individual patients directly. While the study may or may not improve the disease of the patients, they could benefit in the following ways:*

- *Helping others by contributing to medical research*
- *Monitoring of their condition while on the study with additional study services and evaluations.*

*While this investigational agent and regimen are being studied, the ongoing sister studies have shown some early promising results. Preliminary data shows that treatment with this agent may offer benefit by overcoming tumor resistance and trigger response. As a result, this therapy may slow down or stop disease progression. Therefore, Mundipharma-EDO considers the benefit and risk balance to be in favour of further development of this molecule in humans.*

**Item 11:** Very good partial response (VGPR), Synopsis Pg.4; Pg. 34 Section 3.2.1.1

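### Section 7.5.1 lets the next dose level open at engraftment, which can precede Day 30, although escalation, DLT and MTD are all defined on data through Day 30

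*Protocol*

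**What the plan says.** Protocol version 2.0, Section 7.5.1, gives two routes by which a cohort becomes ready for the next dose level: engraftment free of any Grade 3 or higher toxicity, or 30 days without a DLT. The earlier of the two counts. The condition for a three-patient cohort ends "Grade 3 toxicity or through 30 days post-ASCT without a DLT, whichever occurs first, and have safety evaluations performed through that time". The closing note, also in the synopsis, applies the same pair of routes to the last patient: "enrollment in the next dose cohort can begin only when the last patient enrolled in the current dose cohort completes the study through engraftment", with the toxicity condition and the 30-day alternative following. Safety Committee approval is needed in each case.

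The last paragraph of Section 7.5.1 says that "decisions regarding dose escalation will be made based on review of data through Day 30 post-ASCT". Section 7.5.2 states that "DLT is defined as the occurrence of any of the following events occurring within 30 days post-ASCT", subject to at least possible relatedness. Section 7.5.3 allows at most 1 "of 6 patients experiences DLT through 30 days post-ASCT" for a dose to be the MTD. In Section 6.9, "the Safety Committee will review all safety data from all patients enrolled in each cohort to confirm any DLTs", with no minimum follow-up stated for that review.

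**The concern.** A 3+3 rule counts DLTs over a fixed window, and here the window is 30 days. If the next level can open when a patient engrafts, the DLT count used for the decision may be incomplete for that patient. The people at risk are those dosed at the higher level before a late DLT at the current level has appeared.

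The width of the early route turns on an undefined term. Section 7.5.1 refers to Grade 3 or higher toxicity without qualification, whereas Section 7.5.2 specifies organ scope in its own list, for example "Grade 4 non-hematologic toxicity". The clarification memo of 14 December 2018 (Item 10) says that "patients undergoing any high-dose conditioning for transplant, will experience myelosuppression". Sites and the committee could therefore apply the early route differently.

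**Working it through.** **1. Timing.** Under Section 7.5.2 engraftment is delayed only beyond 30 days after ASCT, so it can occur earlier. If it came on Day 14 (assumed), 30 − 14 = 16 days of the DLT window would remain; on Day 10, 20 days; on Day 25, 5 days. Daily inpatient assessment ends at engraftment and discharge, and the next scheduled visit is Day 30 ± 5 (Table 1, footnote 1).

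**2. Which DLTs can fall in the gap.** Delayed engraftment cannot, because the patient has engrafted. QTcF DLTs read from the 24-hour Holter recording cannot, because that recording ends soon after dosing. What remains is Grade 4 non-hematologic events and Grade 3 non-hematologic events outside the exemption list in Section 7.5.2.

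**3. How many patients use the early route.** If Grade 3 toxicity includes cytopenia, the expected myelosuppression probably closes the route to most patients. If it means non-hematologic toxicity only, the route is open to more of them.

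**4. Size, as an illustration.** Section 10.1 says that no formal calculation was done for Phase 1, so there is no plan figure to reproduce. All inputs below are assumptions:

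- p, the true 30-day DLT rate: one third (close to the 33% limit in Section 7.5 for going above 300 mg/m²) or one half.
- L, the share of DLTs arising after engraftment: 25% or 50%.
- f, the share of those late-DLT patients who pass the toxicity filter and are released early: 100%, 50% or 10%.

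A DLT is hidden at a decision with probability pk, where k = L × f. The first three patients are taken as complete by the time of the expansion decision.

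With everyone followed to Day 30, P(escalate) = (1−p)³ + 3p(1−p)² × (1−p)³. At p = 1/3 this is 0.296 + 0.132 = 0.428. At p = 1/2 it is 0.125 + 0.047 = 0.172.

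With only the last patient incomplete at each decision (the third, then the sixth):

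- a = (1−p)² × [1 − p(1−k)], the chance that no DLT is visible in a group of three;
- b = (1−p)² × p × (3−k), the chance that exactly one of the first three has a DLT and it was visible;
- P(escalate) = a + b × a.

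Example: p = 1/3, L = 0.50, f = 1, so k = 0.50. Then a = 0.4444 × 0.8333 = 0.370, b = 0.4444 × 0.3333 × 2.5 = 0.370, and P = 0.370 + 0.370 × 0.370 = 0.508.

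| p | Full Day 30 follow-up | f | L = 25% | L = 50% |
|---|---|---|---|---|
| 1/3 | 0.428 | 100% | 0.469 | 0.508 |
| 1/3 | 0.428 | 50% | 0.449 | 0.469 |
| 1/3 | 0.428 | 10% | 0.432 | 0.436 |
| 1/2 | 0.172 | 100% | 0.210 | 0.246 |
| 1/2 | 0.172 | 10% | 0.176 | 0.180 |

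An upper bound takes every patient as incomplete at his or her own decision. With v = p(1−k), P(escalate) = (1−v)³ × [1 + 3v(1−p)²]. At p = 1/3 and f = 100% this gives 0.56 (L = 25%) or 0.71 (L = 50%); at f = 10% it gives 0.44 or 0.45.

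**5. Accrual.** The synopsis expects 9–12 Phase 1 patients a year: 365/12 = 30 days and 365/9 = 41 days between patients on average. The last-patient case is therefore the realistic one, and the next patient would often be dosed near or after Day 30 in any event.

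**The case against.** The best defense is that the two rules answer different questions. The routes in Section 7.5.1 are permissive and set the earliest point at which enrollment could open; the Day 30 sentence says what the decision rests on; and Section 6.9 has the committee review all cohort safety data first. On that reading approval simply waits for Day 30. The permissive wording is real, and a committee could act this way. But the engraftment route would then have no function as an escalation trigger, and the request for safety evaluations only up to the earlier milestone points the other way. Neither Section 6.9 nor the clarification memos state the reading; the 21 September 2018 memo changes discharge criteria, not escalation.

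The second argument is that the early route is narrow. Up to engraftment its toxicity condition is stricter than the DLT definition: it has no relatedness test and no exemptions, so a Grade 3 infection or mucositis would block early release. On its plain words cytopenia would too. This largely stands, and it is why the effect is probably small. It does not settle which meaning was intended.

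The third argument is slow accrual, required approval, and the committee's power to stop escalation at any time. These reduce the risk without removing it: the accrual figure is an average, up to 18 centers may enroll, and patients 2 and 3 of the initial cohort may enroll together.

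Finally, SAP Section I.C says that the study was halted on safety signals and later discontinued, and that the DLT analysis no longer applies. This limits what a correction can now achieve in this trial.

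**Conclusion.** The conflict is real and should be corrected in the text: the plan's stated basis for escalation is Day 30, and its operating rule can release a cohort sooner. In the realistic case of one incomplete patient, the chance of escalating at a true DLT rate of one third goes from 0.43 to between 0.43 and 0.51. The low end applies if few patients pass the toxicity filter. The late-DLT share and the release share are assumptions that the documents do not inform.

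Three stronger inferences are tempting and are not supported:

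- **That the MTD would be wrong.** DLTs appearing later in the window still count, and six patients are planned at the MTD.
- **That the chance of escalating rises to 0.56–0.71.** Those figures need every late-DLT patient to pass the filter and every patient to be incomplete at once, although Section 7.5.1 enrolls expansion patients one after another and holds the initial cohort until its first patient is cleared. They are a bound, not an estimate.
- **That premature escalation occurred here or contributed to the halt.** Nothing in the documents shows that any escalation took place.

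**What to change.** In Section 7.5.1 and the synopsis, delete engraftment as a trigger for opening the next dose level. Require every patient in the cohort to have completed 30 days post-ASCT, or to have had a DLT, before the Safety Committee approves escalation. This also covers the patient with a DLT, who on a literal reading completes neither of the present routes. If the engraftment branch is kept for the stagger after the first patient of the initial cohort, state whether Grade 3 toxicity there means non-hematologic toxicity only.

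The cost is a short wording change and a wait of up to a few weeks per cohort.

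Only if an escalation took place before the halt, report how many patients had completed Day 30 at each decision. That needs the decision dates, which the SAP does not plan to list, together with the stem cell infusion and engraftment listings already planned in SAP Section VIII.B.

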### **7.5.2. Definition of Dose-limiting Toxicity**

Toxicity will be assessed by the Investigator using the US NCI Common Terminology Criteria for Adverse Events (CTCAE), version 4.03. The centralized laboratory assessment of ECGs will be used for the determination of DLT.

In Phase 1 of the study, DLT is defined as the occurrence of any of the following events occurring within 30 days post-ASCT that are considered by the Investigator to be at least possibly related to tinostamustine:

- Delayed engraftment ( $>30$  days after ASCT). Engraftment will be considered delayed if the subject has not met criteria for both neutrophil and platelet engraftment:
  - Neutrophil engraftment is defined as the first of 3 consecutive days with ANC  $>0.5 \times 10^9/L$ .
  - Platelet engraftment will be defined as the first of 3 consecutive days of platelet count  $>20 \times 10^9/L$  without platelet transfusion in the prior 7 days.
- QTcF  $>500$  msec or  $>60$  msec increase from baseline, with a duration of  $>30$  minutes, based on the mean of triplicate 12-lead ECGs, or  $\geq$ Grade 3 QTcF interval prolongation accompanied by ventricular arrhythmia.

Baseline QTcF interval will be the mean value determined during triplicate ECG(s) at Day -1 (-1), before study drug administration confirmed by the central laboratory.

- Grade 4 non-hematologic toxicity
- Grade 3, non-hematologic toxicity related to treatment, **with the exception of:**
  - Nausea or vomiting
  - Diarrhea
  - Fatigue, dehydration, or glucose intolerance

- Skin rash, dry skin, or pruritus responsive to topical or systemic steroids
- Fever ( $>40^{\circ}\text{C}$  for  $\leq 24$  hours)
- Infection
- Dyspnea, hypoxia, or pneumonitis
- Abdominal pain
- Dysphagia, oral mucositis, oral pain, or anorexia
- Flu-like syndrome
- Engraftment syndrome
- Weight loss
- Pain, pain in extremity, headache, or insomnia
- Hypocalcemia, hypokalemia, hypomagnesemia, hyponatremia, or hypophosphatemia
- Increased aspartate aminotransferase (AST), alanine aminotransferase (ALT), bilirubin, or alkaline phosphatase
- Alopecia

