Definition of DLT Toxicity will be assessed by the Investigator using the US National Cancer Institute (NCI) Common Terminology Criteria for Adverse Events (CTCAE), version 4.03. In Phase 1 of the study, DLT is defined as the occurrence of any of the following events occurring within 30 days post-ASCT that are considered by the Investigator to be at least possibly related to tinostamustine: 

• Delayed engraftment (<math>>30</math> days after ASCT). Engraftment will be considered delayed if the subject has not met criteria for both neutrophil and platelet engraftment:

– Neutrophil engraftment is defined as the first of 3 consecutive days with ANC <math>>0.5 \times 10^9/L</math>.

– Platelet engraftment will be defined as the first of 3 consecutive days of platelet count <math>>20 \times 10^9/L</math> without platelet transfusion in the prior 7 days.

• QTcF <math>>500</math> msec or <math>>60</math> msec increase from baseline, with a duration of <math>>30</math> minutes, or <math>\geq</math>Grade 3 QTcF interval prolongation accompanied by ventricular arrhythmia. Baseline QTcF interval will be the mean value determined during triplicate ECG(s) at Day -1 (-1day), before study drug administration; the mean QTcF will be confirmed by the central laboratory.

• Grade 4 non-hematologic toxicity

• Grade 3, non-hematologic toxicity related to treatment, with the exception of:

– Nausea or vomiting

– Diarrhea

		

Name of Sponsor Mundipharma-EDO GmbH		
Name of Finished Product: Tinostamustine hydrochloride (Formerly EDO-S101)		Name of Active Ingredient: Tinostamustine hydrochloride
Protocol No.: EDO-S101-1004	Temporary (T) No.:	<EUDRACT><IND> No.: CCI [REDACTED]

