11. A triplicate ECG will be performed during Screening to determine patient eligibility for the study. Furthermore, on Day -1, a triplicate ECG is to be performed before study drug administration and a single ECGs will be performed at 30 and 60 minutes after the start of study drug administration for assessment by the site. Another single ECG will be performed at visit on day 30 ( $\pm 5$  days). ECGs are to be repeated by the Investigator, as clinically indicated.
12. Hematology parameters minimally include WBC count and differential (lymphocytes, monocytes, basophils, eosinophils, neutrophils), red blood cell (RBC) count, hematocrit, hemoglobin, and platelet count.
13. Serum chemistry parameters minimally include alanine aminotransferase (ALT), albumin, alkaline phosphatase (ALP), aspartate aminotransferase, (AST), bicarbonate, bilirubin (total, direct, and indirect), calcium, magnesium, chloride, glucose, lactate dehydrogenase (LDH), phosphate, potassium, sodium, and total protein.
14. Urinalysis includes appearance, color, pH, specific gravity, ketones, leukocytes, protein, glucose, bilirubin, urobilinogen, and occult blood.
15. The tinostamustine dose will be administered one day before ASCT (Day -1), at least 24 hours pre-ASCT.
16. Blood samples for PK are to be collected immediately pre-infusion of tinostamustine and 30, 45, and 60 ( $\pm 5$ ) minutes and then at 3, 6, and 24 hours ( $\pm 15$  minutes) and then 48 hours ( $\pm 30$  minutes) after the start of infusion. Blood samples for PK assessment should be collected following the 15-minute supine resting periods described for the continuous Holter recordings. PK samples are to be collected from the arm opposite of that used for tinostamustine administration.
17. On Day 1, ASCs will be administered IV according to standard institutional practice. If the CD34+ product is of large volume, the infusion can be given over 2 days.
18. A skeletal survey (plain radiographs, or any other method used as standard care at the site, of the skull, spine, ribs, pelvis, humeri and femora) will be performed at Screening if not performed within the previous 3 months. Thereafter, skeletal survey and/or other imaging studies are to be performed as clinically indicated.
19. Bone marrow aspirate and trephine biopsy are to be performed during Screening. Bone marrow aspirate and biopsy are to be repeated during treatment as clinically indicated, at the Investigator's discretion, and at any time CR is suspected.

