### **9.2.5. Holter Monitoring**

Continuous Holter monitoring will be performed on Day -1, the day of tinostamustine administration. Holter monitoring will commence 15 minutes prior to the start of the infusion on Day -1 and will continue through 24 hours following the end of infusion.

Patients should be resting comfortably in the supine or semisupine position for 15 minutes prior to each of the following timepoints: 0 [before start of infusion] then after start of the infusion at 15, 30, 45, 60 and 75 minutes and 3, 6, and 24 hours following the start of the infusion.

At time 0 and at all time points after infusion, ECGs readings will be extracted for establishment of baseline and for the purposes of Dose Limiting Toxicities determination and for cardiac safety analyses.

The Holter monitor flashcards will be sent to eResearch Technology, Inc., for processing. The analysis methodology will be described in a separate ECG cardiac safety statistical analysis plan.

Note that because the ECG recordings are stored on flashcards, results will not be available in “real time” at the study center.

The ECGs extracted from the Holter monitoring will be used for the determination of DLTs.

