### **9.2.6. 12-Lead Electrocardiogram**

A triplicate ECG will be performed during Screening to determine patient eligibility for the study. Furthermore, on Day -1 (-1 day), a triplicate ECG is to be performed before study drug administration and a single ECGs will be performed at 30 and 60 minutes after the start of study drug administration for assessment by the site. Another single ECG will be performed at visit on D30 ( $\pm$  5 days). ECGs are to be repeated by the Investigator, as clinically indicated.

ECGs (12-lead) are to be performed in after the patient is supine for 5 minutes.

All screening ECGs will be reviewed centrally. Regarding other 12-lead ECGs: the Investigator or the Sponsor may request expedited central review of ECGs, as clinically indicated. ECGs will be reviewed centrally. The Investigator or the Sponsor may request expedited central review of ECGs, as clinically indicated.

The Investigator’s interpretation of ECGs is to be used for patient management during the study; the central reader interpretation of ECGs extracted from Holter monitoring will be used to determine all ECG data for study endpoints including baseline QTcF interval for cardiac safety analyses and DLTs.

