### 9.2.8.3. Recording Adverse Events

All AEs occurring from the time written informed consent is obtained through the Day 100 ( $\pm 7$  days) visit are to be recorded in the source documents and in the eCRF. AEs will be documented as occurring pre-conditioning (i.e., pre-tinostamustine); during conditioning (i.e., after the start of the first tinostamustine infusion through immediately before the start of ASC infusion); or after ASCT (i.e., after the start of ASC infusion). All AE reports are to contain the following details regarding the AE: a brief description, onset date, duration, intensity, treatment required, relationship to study drug, study drug action taken, outcome, and whether the event is classified as serious.

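### The DLT window in Protocol 7.5.2 and the synopsis is worded as post-ASCT only, which taken literally conflicts with the Day -1 QTc DLT reads and omits brief toxicity between infusion and ASCT (minor, wrong as written)

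*Protocol*

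**What the plan says.** Section 7.5.2 of the Protocol (version 2.0) opens the definition with "DLT is defined as the occurrence of any of the following events occurring within 30 days post-ASCT". The synopsis likewise limits DLTs to events "within 30 days post-ASCT that are considered by the Investigator to be at least possibly related to tinostamustine". The list that follows has four parts: delayed engraftment, QTcF prolongation, Grade 4 non-hematologic toxicity, and Grade 3 non-hematologic toxicity outside a list of exemptions.

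On timing, footnote 15 to the Schedule of Events says: "The tinostamustine dose will be administered one day before ASCT (Day -1), at least 24 hours pre-ASCT". On the QTc criterion, Section 9.2.5 says: "The ECGs extracted from the Holter monitoring will be used for the determination of DLTs". Section 9.2.6 adds that the central reading of "ECGs extracted from Holter monitoring will be used to determine all ECG data for study endpoints", DLTs included. The Holter runs from 15 minutes before the Day -1 infusion to 24 hours after its end.

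In Section 7.5.1 each of the three counting rules refers back to 7.5.2 for what a DLT is. With no DLT in three patients, "then enrollment of the next cohort may commence with approval from the Safety Committee". The MTD in Section 7.5.3 is worded differently, as the highest dose at which at most one of six "patients experiences DLT through 30 days post-ASCT".

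None of the four clarification memos (September, October and December 2018, January 2019) touches the DLT window.

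**The concern.** A conditioning drug's DLT window should open when the drug is given. Here the written window is anchored to the transplant, which comes a day or more later. Two things follow if the sentence is applied as it stands.

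First, the QTc criterion sits inside a post-ASCT window but is measured before ASCT, so 7.5.2 and the ECG sections cannot both be followed to the letter.

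Second, other severe toxicity confined to the interval between infusion and cell infusion would not meet the definition. A severe infusion reaction is the obvious example: the December 2018 memo lists allergic reaction among the possible risks, and it is not as such on the Grade 3 exemption list. For QTc, the ECG sections rescue the intent. For other toxicity, no sentence does so explicitly.

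The DLT tally feeds a 3+3 rule, so every omitted event favours escalation.

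**Working it through.** The plan gives no figure to reproduce. The check is a timeline, a comparison of wording, and an illustration.

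**1. Holter reads against ASCT.** Times are from the start of infusion.
- Section 9.2.5 lists 8 post-start reads: 15, 30, 45, 60 and 75 minutes, and 3, 6 and 24 hours.
- Footnote 9 to the Schedule of Events lists 7, omitting 75 minutes.
- The earliest ASCT is 24 hours after dosing (footnote 15).
- In 9.2.5, 7 of the 8 reads fall before 24 hours and the eighth falls at 24 hours. None falls after the earliest ASCT.
- With a 1-hour infusion, recording could run about 1 hour past an ASCT given exactly 24 hours after the infusion began, but no ECG extraction is scheduled then.
- The only scheduled ECG after ASCT is one single tracing at Day 30 (±5 days). It cannot supply a mean of triplicates or show prolongation lasting more than 30 minutes, both of which 7.5.2 asks for.

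Read literally, then, the QTc criterion is nearly empty.

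**2. Wording side by side.**
- Section 9.2.8.3 separates adverse events during conditioning from those after ASCT. The conditioning period runs "through immediately before the start of ASC infusion); or after ASCT (i.e., after the start of ASC infusion". That vocabulary gives the literal reading some support.
- In the other direction, Section 7.5.1 clears patients, reviews data for escalation, and Section 7.5.3 defines the MTD, all with a period running through Day 30. That fixes an end and is compatible with a start at dosing.
- The same sentence in 7.5.2 is loose elsewhere: engraftment delayed beyond 30 days is listed as an event occurring within 30 days.

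**3. Illustration of direction and scale.** The documents give no infusion-day DLT rate, so both risks below are assumed, and assumed independent. Let p be the post-ASCT DLT risk and r the risk of a non-QTc, non-exempt event that starts and resolves before ASCT. The full-window risk is q = 1 − (1 − p)(1 − r). Under 7.5.1, a dose level escalates with 0 of 3 DLTs, or with 1 of 3 followed by 0 of 3:

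P(escalate) = (1 − q)³ + 3q(1 − q)⁵

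Example: p = 0.10 and r = 0 give 0.729 + 0.3 × 0.59049 = 0.906. With r = 0.01, q = 1 − 0.90 × 0.99 = 0.109 and P = 0.891.

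| r | p = 0.10: q | P(escalate) | drop | p = 0.20: q | P(escalate) | drop |
|---|---|---|---|---|---|---|
| 0 (not counted) | 0.100 | 0.906 | – | 0.200 | 0.709 | – |
| 0.5% | 0.1045 | 0.899 | 0.007 | 0.204 | 0.700 | 0.009 |
| 1% | 0.109 | 0.891 | 0.015 | 0.208 | 0.691 | 0.017 |
| 2% | 0.118 | 0.875 | 0.031 | 0.216 | 0.674 | 0.035 |
| 5% | 0.145 | 0.824 | 0.082 | 0.240 | 0.622 | 0.087 |

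Drops are taken from unrounded values. The sister-study summary in the December 2018 memo (no other meaningful or serious organ toxicity, non-severe gastrointestinal events at the doses studied) and the breadth of the Grade 3 exemptions both favour the low end.

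**The case against.** The best defence is that the literal reading defeats itself. It nearly empties the QTc criterion and makes the engraftment criterion impossible, so it disables two of the four parts of the list. No one would operate the trial that way. The 30-day phrase works naturally as an outer limit, Section 9.2.5 expressly takes Day -1 ECGs for DLT determination, and the QTc baseline in 7.5.2 is itself pre-dose. This stands as evidence of intent, and it is why the point is minor.

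The safeguards also stand:
- Section 6.9 has the Safety Committee review all safety data from every enrolled patient in a cohort.
- Section 7.5 lets it stop escalation at any time, so it is not bound by the tally.
- Section 7.5.1 denies early clearance to a patient with Grade 3 or worse toxicity. That patient could still clear at Day 30 if the event is not classed as a DLT, so this check is partial.

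The gap is also narrow. Toxicity still present after the cell infusion can reasonably be said to occur in the window, and much of a Grade 3 infusion reaction (dyspnea, hypoxia, steroid-responsive rash, brief fever) is exempt anyway.

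The defence does not supply a sentence saying that a non-QTc event before ASCT meets the definition. The committee confirms DLTs against 7.5.2, and an escalation rule should not leave its start date to inference.

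**Conclusion.** Minor, and wrong as written. The defect is confined to the DLT definition in 7.5.2 and its copy in the synopsis. Any error runs towards escalation. Its size cannot be derived from the documents, and given the apparent intent and the committee's powers it is probably small. The table is illustrative only.

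Three stronger inferences are not supported:
- A reader might conclude that Day -1 events were in fact left out of the tally, or that a dose level was wrongly cleared. Nothing in the documents shows this. The SAP (I.C) reports a halt on safety signals but does not link it to the DLT window.
- A reader might extend the fault to the MTD definition. Section 7.5.3 and its synopsis counterpart set only an end point and are sound once the DLT definition is corrected.
- A reader might take the replacement rule in Section 6.1 to remove a dosed patient's DLT from the count. The text does not say so: replacing a patient does not delete that patient's event.

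What is left for analysis is slight. SAP I.C drops the DLT frequency analysis, although the adverse event listing in SAP VIII.A still carries a DLT field.

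**What to change.** In Section 7.5.2 and the synopsis definition of DLT, replace the window phrase with: from the start of the tinostamustine infusion (Day -1) through 30 days post-ASCT. Reword the engraftment bullet in both places as: not engrafted by Day 30 post-ASCT. Section 7.5.3 and the synopsis definition of MTD need no change.

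The cost is two short edits in each of two places. No assessment is added, because adverse events in this interval are already recorded under Section 9.2.8.3 and the Holter reads are already scheduled. The edit also brings the definition into line with Sections 9.2.5 and 9.2.6, and it keeps the wording from being carried into any later protocol that reuses this text.
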